Screening / Pre-vaccine HI titer	Х											
Dispense pharmacy card	S ¹											
IRT transaction	Х	Х	Х	Х	х	Х	Х	Х	Х	Х	Х	
Administration of study drug						Х	Х	Х	Х	Х	Х	
Post vaccine Serum HI titers					X ²							
Drug Accountability Log	S				S			S			S	
Adverse Events / Serious Adverse Events	Х	Х	Х	Х	Х	Х	Х	Х	Х	Х	Х	Х
Subject disposition	Х				Х						Х	

Period	Screening		Investiga	ational Pe	riod		Unscheduled					
Visit Name	Visit 1 Screening	Visit 2 (vaccine status check- in)	Visit 3 (home visit)	Visit 4 (home visit)	Visit 5 EOS1	Visit 6 (home visit)	Visit 7 (home visit)	Visit 8	Visit 9 (home visit)	Visit 10 (home visit)	Visit 11 EOS2	Unscheduled
Day/Week/Month	Week -1	Week 0	Week 1	Week 2	Week 4	Week 8	Week 12	Week 16	Week 20	Week 24	Week 28	
Visit Window Days (d)			± 3d	± 3d	± 3d	± 3d	± 3d	± 3d	± 3d	± 3d	± 3d	
Remote Contact		X ³	S ⁴	S ⁴		S ⁴	S ⁴		S ⁴	S ⁴		

X = assessment to be recorded in the clinical database or received electronically from a vendor

S = assessment to be recorded in the source documentation only

¹ Participants will use the pharmacy card to cover the cost of the influenza vaccine. Participants administered the vaccine from investigator site supply will not receive a pharmacy card. All participants should receive the vaccine within 9 calendar days after the Screening Visit, before the Week 0 visit occurs.

² Post vaccine titer to be drawn before administration of ofatumumab.

³ Remote contact to perform Vaccine Status Check-in by site staff to confirm participant has received the influenza vaccine and to collect any AEs/SAEs.

⁴ Remote contact with participants by site staff. The contact should query about any new AEs or SAEs, changes in con meds and compliance with current treatment. Method of contact can be via telephone, email or text message depending on the preference of each participant

Novartis

Period	Screening Investigational Period							
Visit Name	Visit 1 Screening	Visit 2 (vaccine status check-in)	Visit 3 (home visit)	Visit 4 (home visit)	Visit 5 (home visit)	Visit 6 EOS	Unscheduled	
Day/Week/Month	Week -1	Week 0	Week 1	Week 2	Week 3	Week 4		
Visit Window Days (d)			± 3d	± 3d	± 3d	± 3d		
Obtain informed consent	Х							
Inclusion/exclusion criteria	X							
Demography	X							
Relevant medical history/current medical history	Х							
Prior/Concomitant Medications	X		Χ	Χ	X	Χ	X	
MS Relapse	Х		Х	X	Х	X	Х	
Local Serum Pregnancy Test	S							
Screening / Pre-vaccine HI titer	Х							
Dispense pharmacy card	S ¹							
IRT Transaction	Х	Х	Х	Х	Х	X		
iDMT administration log	Х					Χ		
Post vaccine Serum HI titers						Х		
Drug Accountability log	S					S		
Adverse Events / Serious Adverse Events	Х	Х	Х	Х	Х	Х	Х	
Subject disposition	X					Χ		
Remote Contact		X ²	S ³	S ³	S ³			

Page 35 of 51

Protocol No. COMB157GUS12

X = assessment to be recorded in the clinical database or received electronically from a vendor

S = assessment to be recorded in the source documentation only

¹ Participants will use the pharmacy card to cover the cost of the influenza vaccine. Participants administered the vaccine from investigator site supply will not receive a pharmacy card. All participants should receive the vaccine within 9 calendar days after the Screening Visit, before the Week 0 visit occurs.

² Remote contact to perform a Vaccine Status Check-in by site staff to confirm participant has received the influenza vaccine and to collect any AEs/SAEs.

³ Remote contact with participants by site staff. The contact should query about any new AEs or SAEs, changes in con meds and compliance with current treatment. Method of contact can be via telephone, email or text message depending on the preference of each participant.

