6.7.2 Instruction for prescribing and taking study treatment

All investigational medication will be provided by Novartis. Of atumumab treatment should be administered after study assessments have been completed for the visit.

Influenza Vaccine

The quadrivalent vaccine should be obtained at the patient's preferred pharmacy using the Novartis supplied pharmacy card or will receive the vaccine from the investigational site supply within 9 days of the screening visit.

Ofatumumab

Site staff should remove the study treatment from the refrigerator and allow the auto injector pen to reach room temperature in their unopened box (approximately 15-30 minutes) before self-injection by the participant. Used syringes should be disposed of immediately after use in a sharps container.

A different body site (front of thighs, lower abdomen) should be chosen each time a dose is administered to reduce the risk of an injection-site reaction; investigator/qualified site staff/caregiver can also inject the study treatment in the outer upper arms. Each new injection should be given at least one inch from the previously used site. If administration is in the abdomen, the 2-inch area around navel should be avoided. Study treatment should also not be injected into areas where the skin is tender, bruised, red, or hard, or where the participant has scars or stretch marks.

Participants in Cohort 1

The patients in Cohort 1 will receive their first loading dose of ofatumumab at the study site at Week 2 (2 weeks after receiving the influenza vaccine). The next loading dose of study drug will be dispensed to the participant at this visit to take home for administration at Week 3. The Week 4 dose will be administered in the clinic after the post-vaccine titer is drawn. Doses at Week 3 (dose #2) and Week 4 (dose #3) should be administered +/- 1 day from when they are scheduled to be administered. If the dose on Week 3 (dose #2) is missed, the dose due on Week 4 (dose #3) should be adjusted to 7 days after dose #2 was given.

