Participants should be seen for all visits/assessments as outlined in the assessment schedules or as close to the designated day/time as possible with an allowed visit window of ± 3 days. The Investigator should promote compliance by instructing the subject to attend the study visits as scheduled and by stating that compliance is necessary for the subject's safety and the validity of the study. Missed or rescheduled visits should not lead to automatic discontinuation. The subject should be instructed to contact the Investigator if he/she is unable for any reason to

attend a study visit as scheduled or if he/she is unable for any reason to take the study treatment as prescribed.

Cohort 1: At Week 0, the study site will perform a Vaccine Status Check-in via remote contact to confirm participant has received the influenza vaccine. At-home study visits will be performed at Week 2, 3, 6, 10, 14, and Week 22. Patients and/or caregivers trained to administer the ofatumumab subcutaneous injections will need to administer treatment at home study visits. At Week 4, sufficient study drug will be supplied to the participant to cover all home administrations of study drug until the Week 18 clinic visit. At Week 18, sufficient study drug will be supplied to the participant to cover dosing up at Week 22. The last dose of study drug will be administered at the Week 26 visit at the site. Refer to Table 8-1.

Cohort 2: At Week 0, the study site will perform a Vaccine Status Check-in via remote contact to confirm participant has received the influenza vaccine. At-home study visits will be performed at Week 1, 2, 8, 12, 20, and Week 24. At Week 4, sufficient study drug will be supplied to the participant to cover all home until the next clinic visit (Week 16). At Week 16, sufficient study drug will be supplied to the participant to cover dosing up to and including the Week 24 dose. The last dispensation of ofatumumab supplied in the study will occur at the Week 28 visit at the site. Refer to Table 8-2.

Cohort 3: At Week 0, the study site will perform a Vaccine Status Check-in via remote contact to confirm participant has received the influenza vaccine. At-home study visits will be performed at Week 1, 2 and 3. Refer to Table 8-3.

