Cohort 1 and 2 participants who prematurely discontinue the study while in the Investigational Period should be scheduled for the End of Study (EOS1) visit within 7 days. At this final visit, all the assessments mentioned under EOS1 visit should be performed except for study drug administration. Cohort 3 participants who prematurely discontinue the study while in the Investigational Period should be scheduled for the End of Study (EOS) visit within 7 days.

Cohort 1 and 2 participants who prematurely discontinue the study while in the Extension Period should be scheduled for the final visit of the Extension Period (EOS2) within 7 days. All EOS2 assessments should be performed except study drug administration.

In addition to the scheduled visits, participants may have unscheduled visits due to a MS relapse, an acute illness of undetermined cause, for other reasons, or at the discretion of the Investigator. Data collected during unscheduled visits will be recorded in the unscheduled visits CRF.

Table 8-1 Assessment schedule for participants (cohort 1)

Period	Screening	Inv	estigation	nal Period			6	-month Extens	sion Perio	d		Unscheduled
Visit Name	Visit 1 Screening	Visit 2 (vaccine status check-in)	Visit 3	Visit 4 (home visit)	Visit 5 EOS1	Visit 6 (home visit)	Visit 7 (home visit)	Visit 8 (home visit)	Visit 9	Visit 10 (home visit)	Visit 11 EOS2	Unscheduled
Day/Week/Month	Week -1	Week 0	Week 2	Week 3	Week 4	Week 6	Week 10	Week 14	Week 18	Week 22	Week 26	
Visit Window Days (d)			± 1d	± 1d	± 3d	± 3d	± 3d	± 3d	± 3d	± 3d	± 3d	
Obtain informed consent	Х											
Inclusion/exclusion criteria	Х											
Demography	Х											
Relevant medical history/current medical history	Х											
Prior/Concomitant Medications	Х		Х	Х	Х	Х	Х	Х	Х	Х	Х	Х
MS Relapse	Х		Х	Х	Х	Х	Х	Х	Х	Х	Х	Х
Hepatitis B virus (HBV)	X ¹											
Serum immunoglobulins	X ¹											
Local Serum Pregnancy Test	S											
Screening / Pre-vaccine HI titer	Х											
Dispense pharmacy card	S ²											
Self-injection training			S									
IRT transaction	Х	Х	Х	Х	Х	Х	Х	Х	Х	Х	Х	

Period	Screening	Inv	estigation	nal Period			Unscheduled					
Visit Name	Visit 1 Screening	Visit 2 (vaccine status check-in)	Visit 3	Visit 4 (home visit)	Visit 5 EOS1	Visit 6 (home visit)	Visit 7 (home visit)	Visit 8 (home visit)	Visit 9	Visit 10 (home visit)	Visit 11 EOS2	Unscheduled
Day/Week/Month	Week -1	Week 0	Week 2	Week 3	Week 4	Week 6	Week 10	Week 14	Week 18	Week 22	Week 26	

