Visit Window Days (d)			± 1d	± 1d	± 3d	± 3d	± 3d	± 3d	± 3d	± 3d	± 3d	
Post vaccine Serum HI titers					X ³							
Administration of study drug			X	X	X	Х	Х	Х	X	Х	X	
Drug Accountability	S				S				S		S	
Adverse Events / Serious Adverse Events	Х	Х	Х	Х	Х	Х	Х	Х	Х	Х	Х	Х
Subject disposition	Х				Х						Х	
Remote Contact		X ⁴	S ⁵	S ⁵		S ⁵	S ⁵	S ⁵		S ⁵	S ⁵	

X = assessment to be recorded in the clinical database or received electronically from a vendor

S = assessment to be recorded in the source documentation only

¹ Participants with lab results within the past 6 months prior to screening will not require labs drawn at screening visit. Local labs should be documented in the source. Participants without lab results from the past 6 months prior to screening will require central labs drawn at the screening visit to be entered into the clinical database.

² Participants will use the pharmacy card to cover the cost of the influenza vaccine. Participants administered the vaccine from investigator site supply will not receive a pharmacy card. All participants should receive the vaccine within 9 calendar days after the Screening Visit, before the Week 0 visit occurs.

³ Post vaccine titer to be drawn before administration of ofatumumab.

⁴ Remote contact to perform a Vaccine Status Check-in by site staff to confirm participant has received the influenza vaccine and to collect any AEs/SAEs.

⁵ Remote contact with participants by site staff. The contact should query about any new AEs or SAEs, changes in con meds and compliance with current treatment. Method of contact can be via telephone, email or text message depending on the preference of each participant.

 Table 8-2
 Assessment schedule for participants (cohort 2)

Period	Screening		Investiga	ational Pe	riod		Unscheduled					
Visit Name	Visit 1 Screening	Visit 2 (vaccine status check- in)	Visit 3 (home visit)	Visit 4 (home visit)	Visit 5 EOS1	Visit 6 (home visit)	Visit 7 (home visit)	Visit 8	Visit 9 (home visit)	Visit 10 (home visit)	Visit 11 EOS2	Unscheduled
Day/Week/Month	Week -1	Week 0	Week 1	Week 2	Week 4	Week 8	Week 12	Week 16	Week 20	Week 24	Week 28	
Visit Window Days (d)			± 3d	± 3d	± 3d	± 3d	± 3d	± 3d	± 3d	± 3d	± 3d	
Obtain informed consent	Х											
Inclusion/exclusion criteria	Х											
Demography	Х											
Relevant medical history/current medical history	Х											
Prior/Concomitant Medications	Х		Х	Х	Х	Х	Х	Х	Х	Х	Х	Х
MS Relapse	Х		Х	Х	Х	Х	Х	Х	Х	Х	Х	Х
Local Serum Pregnancy Test	S											

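### Protocol Sections 8 and 6.7.2 disagree on whether Cohort 1 receives the first ofatumumab dose (Week 2) at home or at the study site, and Table 8-1 leans to the site without settling it

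*Protocol*

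**What the plan says.** Three places in the protocol govern the Cohort 1 Week 2 visit.

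- **Section 8, Cohort 1 paragraph.** "At-home study visits will be performed at Week 2, 3, 6, 10, 14, and Week 22". On who injects: "Patients and/or caregivers trained to administer the ofatumumab subcutaneous injections will need to administer treatment at home study visits". On supply, the first step described is at Week 4, when "sufficient study drug will be supplied to the participant to cover all home administrations of study drug until the Week 18 clinic visit"; a second supply at Week 18 covers Week 22. The paragraph ends by referring to Table 8-1.
- **Section 6.7.2, Participants in Cohort 1.** "The patients in Cohort 1 will receive their first loading dose of ofatumumab at the study site at Week 2". The text continues: "The next loading dose of study drug will be dispensed to the participant at this visit to take home for administration at Week 3". Later in the section, the loading-phase remote contact is tied to the second loading dose, with further contacts around the times of home dosing.
- **Table 8-1.** Week 2 is Visit 3, which has no home-visit label. The row "Self-injection training" is marked at Week 2 only. Footnote 5 ("Remote contact with participants by site staff") is marked at Week 2. Drug accountability is marked at Screening and Weeks 4, 18 and 26, but not at Week 2.

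The SAP (Section 1.1) repeats the Week 2, 3 and 4 loading doses without a location, so it does not resolve the question.

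**The concern.** Section 8 and Section 6.7.2 are both instructions that a site would act on, and they put the same dose in two places. It is also the first ofatumumab dose of Cohort 1, the one that Section 6.2.1 singles out when it discusses optional premedication. Three practical matters follow from the location: who is present at the first injection, when the participant is trained relative to it, and how the Week 2 and Week 3 doses reach the participant. About 12 centers are planned, so sites relying on different sections could conduct this visit differently.

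**Working it through.** No plan figure needs reproducing. The check compares the Section 8 list with the columns of Table 8-1 and with the dosing text of Section 6.7.2. Table entries are read by column position.

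**Step 1: which weeks are home visits.**

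| Source | Weeks |
|---|---|
| Section 8, at-home list | 2, 3, 6, 10, 14, 22 |
| Table 8-1, home-visit labels | 3, 6, 10, 14, 22 |
| Table 8-1, remote contact (footnote 5) | 2, 3, 6, 10, 14, 22, 26 |
| Table 8-1, drug accountability | Screening, 4, 18, 26 |
| Table 8-1, self-injection training | 2 |

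The first two rows differ in one item only, Week 2.

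**Step 2: how far Table 8-1 settles it.**

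- The missing home label and the training entry both point to the site.
- Remote contact at Week 2 points to home, but weakly. The mark covers the whole Section 8 list, yet it also stands at Week 26, which Sections 6.7.2 and 8 both place at the site. It therefore does not identify home visits.
- The missing accountability mark says little about location. The row is marked at Screening, before any study drug is scheduled, so it does not track where doses are given. It does sit awkwardly with Section 6.7.2, which dispenses the Week 3 dose at Week 2, and with Section 6.6.1, which requires everything dispensed to be logged.
- The IRT row is marked at every scheduled visit, home or site, so it does not discriminate.

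**Step 3: supply under Section 8 read alone.** Table 8-1 schedules nine doses: Weeks 2, 3, 4, 6, 10, 14, 18, 22 and 26. Weeks 4, 18 and 26 are site visits (3 doses). The Week 4 supply covers Weeks 6, 10 and 14 (3 doses), and the Week 18 supply covers Week 22 (1 dose). That accounts for 3 + 3 + 1 = 7, leaving 9 − 7 = 2 doses, Weeks 2 and 3, with no supply step in that section. Section 6.7.2 accounts for both through a Week 2 site visit.

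**Step 4: training under each reading.** If Week 2 is a site visit, the Week 2 training precedes the first home dose at Week 3. If Week 2 is a home visit, the earlier visits are Screening and the remote Week 0 check-in, and neither is marked for training, although Section 8 requires a trained injector at home.

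**The case against.** The strongest reply is that the documents largely contain the ambiguity. Section 8 requires visits to follow the assessment schedules and sends the reader to Table 8-1, which does not call Week 2 a home visit. The only scheduled training is at Week 2, and Section 6.7.2 links the loading-phase remote contact to the second dose, not the first. A site reading Section 8 literally would soon meet the table. This stands, and it makes undetected divergence between sites less likely. It does not remove the conflict, because the Section 8 sentence remains operative and contradicts Section 6.7.2 outright.

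Three stronger readings are tempting and are not supported:

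- **That Table 8-1 supports both settings equally.** The label and training entries favour the site. The two entries on the other side are weak or indirect.
- **That drug supply is contradictory.** Section 8 is silent on the Week 2 and Week 3 supply; it states no competing route. Section 6.7.2 states one, its supply text for later doses agrees with Section 8, and Section 6.1.1.1 permits direct shipment to participants. A home dose at Week 2 could therefore be supplied; the route is simply not described for that visit.
- **That early reactions would be captured differently.** Table 8-1 marks adverse event collection at Week 2 in either setting, and Section 10.1.1 requires questioning at each visit.

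**Conclusion.** The point holds as an internal inconsistency about the location of one dose. Section 8 places the Cohort 1 Week 2 dose at home, Section 6.7.2 places it at the study site, and Table 8-1 leans to the site without fully settling it. The reach is one of nine scheduled Cohort 1 doses, in up to 22 participants. What is at stake is supervision of the first injection and the order of training and dosing; the supply description for Weeks 2 and 3 needs to follow whichever location is stated. There is no effect on the titer estimate: seroprotection and seroconversion are assessed at Week 4 and summarized by cohort, and neither definition uses the place of dosing.

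The conclusion rests on the current text of Sections 6.7.2 and 8. The secondary observations also assume that the columns of Table 8-1 survived text extraction, and they should be confirmed against the source table. Nothing here establishes which setting was intended.

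**What to change.** Reconcile Section 6.7.2, the Cohort 1 paragraph of Section 8, and Table 8-1 so that all three state one location for the Week 2 dose. Then align four items with it: the Visit 3 label, the timing of self-injection training, the remote-contact and drug-accountability entries at Week 2, and the description of how the Week 2 and Week 3 doses are supplied. The choice of setting belongs to the sponsor.

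The cost is about one sentence and a few table cells. Section 14.1 requires a written, approved amendment, so the correction is most easily carried with the next one. No analysis, sample size or SAP text changes.

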8.1 Rescreening

Rescreening is not permitted.

8.2 Information to be collected on screening failures

Participants who sign an informed consent form and subsequently found to be ineligible prior to enrollment will be considered a screen failure. The reason for screen failure should be recorded on the appropriate Case Report Form. The demographic information, informed consent, and Inclusion/Exclusion pages must also be completed for screen failure participants. No other data will be entered into the clinical database for participants who are screen failures, unless the participant experienced a serious adverse event during the screening phase (see SAE section for reporting details). If the participant fails to be enrolled, the IRT must be notified within 2 days of the screen fail that the participant was not enrolled.

Participants who are enrolled and fail to start treatment, e.g. participants enrolled in error, will be considered an early terminator. The reason for early termination should be recorded on the appropriate Case Report Form.

8.3 Participant demographics/other baseline characteristics

Participant demographic data and baseline characteristics to be collected on the participants include: age, sex, race and ethnicity. Relevant medical history/current medical condition data includes data collected up to the point in which informed consent is signed. Where possible, diagnoses, and not symptoms will be recorded. Investigators will have the discretion to record abnormal test findings on the CRF capturing medical history whenever in their judgment, the test abnormality occurred prior to the informed consent signature.

8.4 **Efficacy**

Not applicable.

8.5 MS Relapse

Participants must be instructed to immediately report new neurological symptoms, re-occurring or worsening of previous symptoms to the Investigator. If a participant reports symptoms that may be consistent with relapse, an unscheduled visit to the Investigator must be scheduled as soon as possible (whenever possible within 7 days of onset of the symptoms). Confirmed relapses should be recorded on the Summary of MS Relapse eCRF.

MS relapse definition

An MS relapse is defined as an appearance of a new neurological abnormality or worsening of previously stable or improving pre-existing neurological abnormality, separated by at least 30 days from onset of a preceding clinical demyelinating event (Polman et al 2011). The abnormality must have been present for at least 24 hours and occurred in the absence of fever $(< 37.5^{\circ})$ C) or a known infection.

8.5.1 Laboratory evaluations

A central laboratory will be used for analysis of all specimens collected listed below with the exception of the serum pregnancy test. Details on the collection, shipment of samples and reporting of results by the central laboratory are provided in the laboratory manual.

Hepatitis B virus (HBV) 8.5.1.1

Hepatitis B virus (HBV) will be performed at Visit 1/Screening for participants in Cohort 1 that do not have test results in their medical history within 6 months prior to the Screening Visit/Week -1.

8.5.1.2 Serum Immunoglobulins

Serum immunoglobulins will be performed at Visit 1/Screening for participants in Cohort 1 that do not have test results in their medical history within 6 months prior to the Screening Visit/Week -1.

8.5.2 Pregnancy and assessments of fertility

A local, serum pregnancy test will be performed for all women of child-bearing potential at Screening Visit/Week -1.

The Investigator should review the contraception status with the participant at the Screening Visit/Week -1 to ascertain if the participant will comply with protocol requirements for highly effective contraception.

All pre-menopausal women who are not surgically sterile will have pregnancy testing.

Additional assessments 8.6

No additional tests will be performed on participants entered into this study.

9 Study discontinuation and completion

